6.5. Multicenter Studies

This study will be conducted by multiple investigators at multiple sites internationally. Randomization to treatment groups will not be stratified by country. However, the countries will be categorized into geographic regions:

- Geographic Region Subgroups: North America, Asia (Japan) and Rest of World (incl. EU, Australia, and NZ)

Unless otherwise specified, the statistical analysis models will adjust for geographic region. For analysis of primary endpoints, the presence of a treatment-by-geographic region interaction will be tested at a .10% significance level. Treatment group comparisons for the primary outcomes will be presented separately for each geographic region. Where there is evidence of an interaction (p -value $< .0.10$), graphical inspection of descriptive statistics will be used to assess whether the interaction is quantitative (i.e., the treatment effect is consistent in direction but not size of effect) or qualitative (the treatment is beneficial for some but not other regions). In addition, further investigations through additions of baseline covariates of statistical models will be performed in an attempt to explain the interaction in terms of patient characteristics.

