6.1	
 • Updated parties responsible for TFL generation. • Added Follow up Period to list of study periods. • Clarified wording around study periods (from treatment periods). • Doses for Extension Period – Induction in Table 1 changed from 600 mg to 1000 mg

Section	Summary of Changes
	
 • Clarified Dose labels in Table 1 to not include combined period labels. • Description of how to reset placebo group baseline when entering the extension period modified. “assessment prior to the date of first injection” changed to “assessment on or prior to the date of first injection” • Added wording to clarify that not all analyses mentioned in the SAP will necessarily be created in a static display.
6.2	Added flexible wording around the possibility of a Per Protocol population.
6.4	Wording added to reference the new Appendix B (IBDQ Missing Data Algorithm)
6.4.2	Clarified use of mBOCF for health outcomes analyses is limited to PGI-S and IBDQ.
6.4.3	Added section for LOCF.
6.4.4	Removed “follow-up emergent” AE language and section number change.
6.5	Changed the interaction p-value criteria to 0.10 from 0.05.
6.6	Changed references for the graphical procedure.
6.8	Changed randomization date to informed consent date for calculation of age
6.10	
 • Added wording around screening period concomitant medication summary. • Changed Concomitant Medication start date definition to Informed Consent date from first dose date. • Removed wording describing an analysis of prior Concomitant Medications and current Concomitant Medications.
6.11.5	
 • Added additional exploratory efficacy endpoints which were not previously described in the protocol. • Added Reference to UCEIS. • Added a definition of time to response and duration of response. • Added censoring rules for time to event endpoints.
6.12	Added “6.12.1 Secondary Health Outcomes Endpoints” heading.
6.14	
 • Added wording regarding the formal statistical testing of safety data.

Section	Summary of Changes
	
 • Clarifying wording added and certain analyses removed per Safety Analytics guidance. • Description of how to reset placebo group baseline when entering an extension period changed from “prior to the first injection” to “on or prior to the first injection”

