5.2. Determination of Sample Size

Approximately 240 patients will be randomized to 1 of 4 double-blind treatment regimens to evaluate the primary endpoint. Patients will be randomized to placebo, 50 mg LY3074828 Therapeutic Drug Monitoring (TDM), 200 mg LY3074828 TDM, or the 600 mg LY3074828 fixed-dose treatment group in a 1:1:1:1 ratio (60 patients per arm). The randomized patients will be comprised of approximately one-third biologic-naïve patients (~20 per arm) and approximately two thirds patients who have been exposed previously to at least 1 biologic agent (~40 per arm).

Assuming LY3074828 and placebo clinical remission rates of 30% and 7.5% respectively (a difference of 22.5%) and given 60 patients per treatment arm, each pairwise comparison testing

the superiority of LY3074828 to placebo will have 89% power via chi-square test with a two-sided 0.05 significance level.

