6.15.1. Efficacy Subgroup Analysis

Subgroup analyses will be conducted for the following efficacy assessments:

- Clinical Remission at 12 weeks

Subgroups to be evaluated include the following:

- Patient Demographic Subgroups:
 - Gender: female or male
 - Age group: < 65 years, ≥65 years
 - Race: American Indian/Alaska Native, Asian, Black/African American, Native Hawaiian/Other Pacific Islanders, White, or Multiple Races
 - Ethnicity: Hispanic/Latino, Non-Hispanic/Non-Latino
 - Weight: <100 kg or ≥100 kg
 - Weight: <80 kg, ≥80 and <100 kg, or ≥ 100 kg

- Body mass index (BMI, kg/m^2) category (underweight ($<18.5 \text{ kg/m}^2$); normal (≥ 18.5 and $<25 \text{ kg/m}^2$); overweight (≥ 25 and $<30 \text{ kg/m}^2$); obese (≥ 30 and $<40 \text{ kg/m}^2$); or extreme obese ($\geq 40 \text{ kg/m}^2$))
- Geographic Region Subgroups:
 - Geographic region: North America, Asia (Japan) and Rest of World (incl. EU and Australia, NZ)
- Prior/Concomitant UC Therapy:
 - Prior Biologic therapy vs Biologic Naïve
 - Concomitant UC Baseline Medication:
 - Corticosteroid current use (concomitant use of any medications with ATC codes A07EA, H02AB, A01AC) vs none
 - 5 ASAs current use (concomitant use of any medications with ATC code A07EC) vs none
 - Thiopurines current use (e.g. azathioprine; concomitant use of any medications with ATC code L01BB, LO4AX (where Preferred name= “AZATHIOPRINE”)) vs none
 - More than one of the above
- Baseline Severity Groups:
 - Mayo score at baseline (6-8, 9-12)
 - CRP: 6 mg/L, $>6 \text{ mg/L}$
- Other Baseline Patient Characteristics Subgroups:
 - Smoking status at baseline: yes or no
- Therapeutic Drug Monitoring Subgroup
 - TDM adjustment status: yes or no

For Week 12 Clinical Remission analyses, a logistic regression model with treatment, subgroup, and the interaction of treatment-by-subgroup included as factors will be used. The treatment-by-subgroup interaction will be tested at the significance level of 0.10. Treatment group differences will be evaluated within each category of the subgroup using Fisher’s exact test, regardless of whether the interaction is statistically significant. Missing data will be imputed using NRI, as described in Section 6.4.1. If any group within the subgroup (for example, yes, no) is less than 10% of the total population, only descriptive statistics will be provided for that subgroup (that is, no inferential testing).

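### SAP 6.5 prints the region-interaction level as .10% where 0.10 is meant, and with about 4.5 expected placebo remitters an ordinary logistic interaction test is unreliable, so a non-significant result is not evidence of regional consistency

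*SAP*

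**What the plan says.** **Region (SAP 6.5).** For the primary endpoint, "the presence of a treatment-by-geographic region interaction will be tested at a .10% significance level". Two sentences later the action rule begins "Where there is evidence of an interaction", and its bracketed threshold is printed as p < .0.10, evidently 0.10. If the rule is met, descriptive graphs are used to judge whether the interaction is quantitative or qualitative, and covariates are added to try to explain it. Between these two statements, 6.5 also promises treatment comparisons separately by region, with no condition on the p-value.

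**Revision history (SAP Section 3, entry for 6.5).** "Changed the interaction p-value criteria to 0.10 from 0.05".

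**Subgroups (SAP 6.15.1).** "The treatment-by-subgroup interaction will be tested at the significance level of 0.10", from a logistic model with treatment, subgroup and their interaction. Fisher's exact test is applied within each category whatever the interaction result. If a category holds under 10% of patients, that subgroup is described only. Region is one of the listed subgroups.

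**Event rates (SAP 5.2).** "Assuming LY3074828 and placebo clinical remission rates of 30% and 7.5% respectively", with 60 patients in each of four arms.

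Neither 6.5 nor 6.15.1 says whether the interaction test is Wald, likelihood-ratio or penalised, or what happens when a cell has no remitters. SAP 6.5 also does not say whether all four arms enter one model or each dose is compared with placebo in turn.

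**The concern.** There are two separate problems.

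The first is a decision threshold printed two ways in one paragraph, a hundredfold apart if the first is taken literally.

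The second would remain after the misprint is corrected. A logistic interaction model needs events in every arm-by-region cell, and the placebo arm is expected to supply fewer than five in all. When a cell has no remitter, the maximum-likelihood interaction estimate runs to infinity. Its standard error grows faster still, so the Wald statistic shrinks towards zero and p towards 1. The likelihood-ratio statistic stays finite, but its chi-square reference is poor in such sparse data. Because the SAP names no test, a software default could settle the answer. The 10% rule in 6.15.1 does not guard against this, since it counts patients and not events.

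At stake is how the regional result is read. The p-value in 6.5 triggers the quantitative/qualitative assessment and the search for an explanation, and a non-significant result is easily reported as consistency.

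**Working it through.** **1. The plan's own figure.** Inputs from SAP 5.2: 30% vs 7.5%, 60 per arm, two-sided 0.05. The pooled rate is 0.1875.
- Null SE = √(2 × 0.1875 × 0.8125 / 60) = 0.0713.
- Alternative SE = √((0.30 × 0.70 + 0.075 × 0.925) / 60) = 0.0682.
- Power = Φ((0.225 − 1.96 × 0.0713) / 0.0682) = Φ(1.25) = 89%.

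The stated 89% reproduces. No power is stated for any interaction test.

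**2. The threshold.** Literal reading of 6.5: .10% = 0.001. Against it stand the action rule in the same paragraph (0.10), the revision entry (0.10 from 0.05) and 6.15.1 (0.10). Three places agree, so .10% is a misprint.

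**3. Placebo events by region.** Expected total: 60 × 0.075 = 4.5. Shares are assumed. The chance that a region with n placebo patients has no remitter is 0.925ⁿ.
- 40/15/45% (n = 24, 9, 27): 1 − (1 − 0.925²⁴)(1 − 0.925⁹)(1 − 0.925²⁷) = 62.5% that at least one region has none.
- Equal thirds (n = 20 each): 1 − (1 − 0.925²⁰)³ = 51%.

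A 15% region passes the 10% patient rule (36 of 240), yet it expects 9 × 0.075 = 0.7 placebo remitters and has none with probability 0.925⁹ = 50%.

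**4. Behaviour of the tests.** Simulated 240-patient trials, four arms by three regions, 6-df interaction, nominal level 0.10, both share sets. In the alternative, active arms have 7.5% remission in one region (the 45% region under 40/15/45) and 40% in the other two; placebo is 7.5% everywhere. Some arm-by-region cell is empty in roughly 50-75% of trials.

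| Test | No interaction | No effect in one region |
|---|---|---|
| Wald | 2-4% | 4-7% |
| Likelihood-ratio, unpenalised | 12-15% | 35-43% |
| Firth-penalised likelihood-ratio | 6-7% | 23-29% |

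Entries are approximate ranges over repeated runs, with and without prior biologic use in the model. Monte Carlo error is about 2 points at worst: for 500 trials at 26%, √(0.26 × 0.74 / 500) = 0.020.

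**5. Sensitivity.**
- *Plan's rate elsewhere:* 30% on active outside the no-effect region, tested as a four-arm, one-dose-vs-placebo or pooled-dose model, with shares from equal thirds to 20/10/70. Likelihood-ratio power is about 15-42% and Wald about 0.5-18%. At a literal 0.001 these fall to at most 3% and about 0%.
- *Overall active rate held at 30%:* likelihood-ratio power is 19-50% when the no-effect region holds 15-40% of patients. With a 55% no-effect region, the others need (0.30 − 0.55 × 0.075) / 0.45 = 57.5% remission. Likelihood-ratio power is then 59-69% and Wald 19-42%.
- *Prior-biologic subgroup (1/3 : 2/3), no effect in one stratum:* likelihood-ratio 33-47%, Wald 8-35%.

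**The case against.** **A reader might infer that the test cannot work.** The documents do not support that. It fits only a Wald test in a 6-df model, and the SAP specifies neither. Protocol 12.2.6.1 tests each arm against placebo separately, so a 2-df test is equally plausible. The unpenalised likelihood-ratio test does reject, though part of its 35-43% reflects a null rate of 12-15%.

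**A reader might infer that the misprint causes the low power, or that the test would be run at 0.001.** The rejection rates in the table are all at 0.10, so the misprint contributes nothing to them. The surrounding text makes 0.10 clear, and the misprint does not extend to 6.15.1.

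**A reader might infer that a region with no effect would go unnoticed.** It would still be displayed. SAP 6.5 shows regional comparisons whatever the p-value, and 6.15.1 runs Fisher tests within categories, which stay valid with zero cells (if a category is under 10%, that subgroup is descriptive only). SAP 6.1 and 6.11.1 provide 95% confidence intervals for treatment differences, though not explicitly by region. Only the graphical and covariate follow-up depends on the test.

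**The alternative is a chosen one.** With 40% remission outside a 45% no-effect region, the overall active rate is 0.55 × 40% + 0.45 × 7.5% = 25.4%, not the plan's 30%. Some patterns give likelihood-ratio power above 50%, as step 5 shows. This stands, and it means the exact rejection rates are illustrative.

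**Low interaction power is ordinary at 60 per arm, and the checks are supportive.** Also true. They do not enter the primary test or the sequential procedure in SAP 6.6. What remains is an unnamed test whose null rejection rate is well below or above nominal according to which default is used.

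**Conclusion.** The point holds in two parts.

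The .10% in SAP 6.5 is a misprint for 0.10. This is certain from the documents and easily corrected.

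The interaction test, as left unspecified, is unreliable at the plan's own event rates. In the four-arm model at a nominal 10%, the null rejection rate is about 2-4% by Wald and 12-15% by likelihood-ratio. When one region has no effect at all, the test misses it in about 93-96% of trials by Wald and 57-65% by likelihood-ratio. A non-significant result therefore says little about regional consistency.

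The event count rests on the SAP's 7.5% and 60 per arm. The rejection rates rest on assumed region shares, an assumed model form and a chosen effect pattern. The miscalibration appeared under both share sets; the power figures move with the scenario. The consequence is limited to exploratory consistency checks.

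**What to change.** 1. In SAP 6.5, print 0.10 in both places, in the form used in 6.15.1.
2. In 6.5 and 6.15.1, fit the interaction models with Firth-penalised likelihood and name the penalised likelihood-ratio test. Naming the test matters: in the prior-biologic check, Firth estimates with a Wald test rejected only 4-4.5% under no interaction in the dose-vs-placebo and pooled models. State also whether the model has four arms or is pairwise.
3. State that the test is exploratory with low power, and that a non-significant result is not evidence of consistency.
4. Report region-specific remission differences for each dose against placebo with confidence intervals, and base the quantitative/qualitative assessment on them whatever the p-value.

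The cost is SAP wording, a standard software option and slight extra analysis work. Conduct and the primary test are unaffected. The penalised test does not solve the power problem: it is still somewhat conservative (about 6-7% at nominal 10%) and, at about 23-29%, would miss the no-effect region in most trials. That is why the estimates should lead.

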6.6. Multiple Comparisons/Multiplicity

The primary endpoint will be tested by using the primary analysis of categorical efficacy method, as described in section 6.1.

[figure not shown]
A graphical multiple testing procedure [1][2] for the primary objective will be implemented to control the family-wise type I error rate at a 2-sided α level of 0.05. In this particular application, the α levels for the p -values associated with each comparison are computed at each step depending on the outcomes of the preceding significance tests. The graphical approach is a closed testing procedure; hence, it strongly controls the family-wise error rate (Alosh et al. 2014 [2]).

There are 3 comparisons to be tested:

- Comparison 1 – Proportion of 600 mg patients achieving Clinical Remission at 12 weeks compared with placebo
- Comparison 2 – Proportion of 200 mg TDM patients achieving Clinical Remission at 12 weeks compared with placebo
- Comparison 3 – Proportion of 50 mg TDM patients achieving Clinical Remission at 12 weeks compared with placebo

Comparison 1 will first be tested at 2-sided $\alpha = 0.05$. If successful, the test for Comparison 2 will be performed at 2-sided $\alpha = 0.05$. If successful, the test for Comparison 3 will be performed at 2-sided $\alpha = 0.05$. If at any point a comparison fails to meet the significance threshold, the test will stop.

Figure 3 Illustration of Graphical Multiple Testing Procedure with Initial α Allocation and Weights.

Unless otherwise specified, there will be no adjustment for multiple comparisons for any other analyses.

6.7. Patient Disposition

All patients who discontinue from the study will be identified, and the extent of their participation in the study will be reported. If known, a reason for their discontinuation will be given.

Counts and percentages of patients entered and patients failing screening before randomization will be summarized overall, and counts and percentages of patients randomized, discontinued, and completed will be summarized by treatment group. The reasons for discontinuation from treatment and from the study will be summarized by treatment group.

Summaries of patient disposition will be based on all patients screened in the study. The number of patients in each of the analysis populations will be displayed. The reasons for discontinuation will be summarized. A listing of patients excluded from any population, if any, will be provided along with the reason for the exclusion.

6.8. Patient Characteristics

The patient's year of birth, sex, weight, height, smoking habits, previous biologic treatment, and other demographic characteristics are collected at the screening visit. Age and body mass index will be calculated.

Only the year of birth is collected at screening. For the purpose of age calculation, the month and day of birth will be imputed as July 01, of the year of birth. Age is computed as follows;

$$\text{Age} = (\text{Informed Consent Date} - \text{Date of Birth} + 1) / 365.25.$$

Demographic and baseline characteristics (including age, gender, race and ethnicity) will be summarized for each treatment group.

Certain characteristics, that are collected at baseline or after baseline but not summarized in the demographic summary, will be reported as a listing.

No inferential analysis for the comparability of baseline covariates across treatment groups will be performed.

6.9. Treatment Compliance

Adequate study drug compliance is defined in Section 9.10 of the protocol.

Study treatment administration and compliance will be listed for all entered patients. The number and percentage of patients treatment compliant by week (that is, at each injection time point) will be summarized by treatment group for each treatment period.

No patient will be excluded from the ITT population as a consequence of significant noncompliance.

A listing of the treatment-noncompliant patients will be presented by treatment arm.

6.10. Concomitant Therapy

For the purposes of subgroup identification, medications will be classified into anatomical therapeutic chemical (ATC) drug classes using the latest version of the World Health

Organization (WHO) drug dictionary. Summaries of Concomitant and Prior medication will utilize WHO drug preferred names.

Medication start and stop dates will be compared to the date of first dose of treatment in each treatment period to allow medications to be classified as Concomitant for each treatment period. Concomitant medication use that starts and stops during the baseline/screening period will be included in summaries of the induction period.

Prior medications are those medications that start and stop prior to the date Informed Consent (IC). Concomitant medications are those medications that start after the IC date. Concomitant medications are assigned to the treatment period in which they are actually ongoing. For example, if a patient is receiving concomitant medication during the Induction Dosing Period but has a stop date during the Induction Dosing Period, the same medication would not be listed as a concomitant medication during the latter periods unless patient has a new start date.

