7.1. Summary of Study Design

Study I6T-MC-AMAC is a multicenter, randomized, double-blind, parallel-arm, placebo-controlled trial in which approximately 240 subjects will be randomized (Figure AMAC.7.1). Subjects must have moderate or severe UC (defined as a Mayo score of 6 to 12 with an endoscopic subscore ≥ 2 ; see Attachment 5). Approximately two-thirds (~160) of the subjects randomized to study treatment must have been exposed to at least 1 previous biologic therapy (received treatment with 1 or more agents such as tumor necrosis factor [TNF] antagonists, vedolizumab, or experimental UC biologic therapy), and approximately one-third (~80) of the subjects will be naive to biologic therapy.

All procedures to be conducted during the study, including timing of all procedures, are indicated in the study schedule (Attachment 1).

Screening Period

Subjects will be evaluated for study eligibility ≤ 28 days before the baseline visit. At the baseline visit, subjects who fulfill the eligibility criteria will be randomized equally to 1 of 4 induction treatment arms.

Subjects may be rescreened upon review and consultation with a member of the Lilly medical team.

Induction Period

A 12-week induction period is designed to establish the efficacy and safety of LY3074828 administered IV at Weeks 0, 4, and 8 (described in Section 10.1 and Section 10.3, respectively). Approximately 240 subjects will be enrolled into 4 induction treatment arms (placebo or 50 mg, 200 mg, or 600 mg of LY3074828) to adequately evaluate the clinical response and remission endpoints. On the basis of plasma concentrations of LY3074828 during the induction period, dose levels in individual subjects within the 50-mg and 200-mg arms may be increased (Section 9.1) and will be communicated to the site by the sponsor. The 600-mg dose arm will remain at a fixed dose during the induction period. No subject will be dosed above 600 mg in this initial induction period. Subjects enrolled in the trial will be stratified across the treatment arms on the basis of previous exposure to biologic therapy for treatment of UC.

Subjects who discontinue the study for any reason before the end of the induction period will complete the induction period early termination visit (V7).

Maintenance Period:

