9.9. Concomitant Therapy

All concomitant medication taken during the study must be recorded on the concomitant medication case report form (CRF).

All subjects should maintain their usual medication regimens for concomitant conditions or diseases throughout the study unless those medications are specifically excluded in the protocol.

Subjects taking concomitant medications should be on stable dosages at the time of baseline and should remain at stable dosages throughout the study unless changes need to be made because of AEs. Additional systemic drugs are to be avoided during the study, unless required to treat AEs. Other medications may be allowed if they are approved by the sponsor or its designee.

Uses of nonlive (inactivated) vaccinations are allowed for all subjects. Use of live, attenuated vaccines is prohibited. Chronic use of nonsteroidal anti-inflammatory drugs during the study is excluded. Chronic use of opioid drugs during the study is excluded. Occasional use of acetaminophen in over-the-counter dose ranges for headache, menstrual pain, or other transient conditions is acceptable but should be held on study visit days until after assessments have been completed, as much as possible; use of prophylactic daily aspirin (up to 162.5 mg) is permitted.

Concomitant therapies for treatment of UC during the study are permitted only as outlined in [Table AMAC.3](#).

Table AMAC.3. Permitted Medications for Treatment of Ulcerative Colitis

Drug Class	Conditions for Use
Oral 5-ASA or sulfasalazine	Subjects were receiving the medications at baseline and the prescribed dose was stable for at least 2 weeks before screening endoscopy. Dosages should remain stable throughout the study unless the medication is discontinued because of toxicity. If stopped, the medication should not be restarted during the study.
Azathioprine or 6-mercaptopurine	Subjects were receiving the medications at baseline and the prescribed dose was stable for at least 8 weeks before baseline. Dosages should remain stable throughout the study unless the medication is discontinued because of toxicity. If stopped, the medication should not be restarted during the study.

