6.4.3. Modified Baseline Observation Carried Forward

An mBOCF analysis will be performed on key continuous efficacy and the PGI-S and the IBDQ.

This is both a sensitivity analysis, and an analysis for regulatory agencies that prefer this approach. For patients discontinuing investigational product due to an AE, the baseline observation will be carried forward to the corresponding primary endpoint for evaluation. For patients discontinuing investigational product for any other reason, the last non-missing post-baseline observation before discontinuation will be carried forward to the corresponding primary endpoint for evaluation. Randomized patients without at least one post-baseline observation will not be included for evaluation with the exception of patients discontinuing study treatment due to an AE.

6.4.4. Missing Data Imputation for Adverse Event, Concomitant Medication Dates, and Laboratory Values

If a medication date or AE date is completely or partially missing, the following imputation rules should be utilized in the analysis unless otherwise stated:

- For the start date:
 - If year, month, and day are missing then use the earlier of the patient's first visit date or the consent date.
 - If either month or month and day are missing then use January 1.

- If only day is missing, impute the first day of the month.
- For the start time:
 - Impute as 23:59.
- For the end date:
 - If year, month, and day are missing then use the patient's last visit date.
 - If either month or month and day are missing then use December 31.
 - If only day is missing then use the last day of the month.
 - The imputed date will not be beyond the patient's last visit date.

If there is any doubt for the start and end date/times for AEs, the event will be flagged as treatment-emergent. For medications, the medication will be flagged as concomitant.

Laboratory parameters will be summarized based on the available data at each time point and no imputation is proposed in this document.

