6.18. Changes to the Planned Analysis from the Clinical Study Protocol

The primary analysis method for categorical variables will now be logistic regression not CMH.

Prior Concomitant and Current Concomitant medication will not be summarized as reported in section 12.2.4 of the protocol. Prior Medication and Concomitant medications will be summarized per section 6.10 of the SAP.

As of the approval date of SAP version 3, there are no additional changes to the planned analysis in the protocol.

7. Unblinding Plan

A limited number of pre-identified individuals at Eli Lilly and Company may gain access to the unblinded data as part of the prespecified interim analysis (see section 6.17) in order to initiate the final population PK/PD model development processes for primary analyses and/or to evaluate safety data. Information that may unblind the study during the analyses will not be reported to study sites until the Maintenance period has been completed.

Additionally, a limited number of pre-identified individuals, an Eli Lilly and Company PK/PD Scientist and unblinded site pharmacists will have access to patients dosing information in order to conduct the TDM adjustments. Unblinded dosing information will not be shared with any other study or site personnel.

8. References

- [2] Frank-Bretz et al., Graphical approaches for multiple comparison procedures using weighted Bonferroni, Simes or parametric tests,, *Biometric Journal* 53 (2011) 6, 894-913. Al
- [2]. Mohamed Aloh et., Advanced multiplicity adjustment methods in Clinical trials,, *Statistics in Medicine*, Published on line 16 September 2013 in Wiley Online Library.
- [3]. Mosli M et al., Development and validation of a histological index for UC, *Gut* 2015, 0:1-9.
- [4]. Travis et al., Developing an instrument to assess the endoscopic severity of ulcerative colitis: the Ulcerative Colitis Endoscopic Index of Severity (UCEIS), *Gut* 2012, 535-42.

9. Appendices

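### SAP 6.10 contradicts itself on background therapy: by its definitions, a drug begun by the consent date and still taken is neither prior nor concomitant

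*SAP*

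**What the plan says.** SAP 6.10 contains four statements that bear on how a drug is classified:

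- Prior: "Prior medications are those medications that start and stop prior to the date Informed Consent (IC").
- Concomitant: "Concomitant medications are those medications that start after the IC date".
- A comparison with dosing: "Medication start and stop dates will be compared to the date of first dose of treatment in each treatment period", so that drugs can be classed as concomitant for each period.
- An allocation rule: "Concomitant medications are assigned to the treatment period in which they are actually ongoing".

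SAP 6.18 sets aside the medication summaries of protocol 12.2.4 and makes this section the rule: "Prior Medication and Concomitant medications will be summarized per section 6.10 of the SAP". SAP 6.15.1 then builds subgroups of Week 12 clinical remission from current use of corticosteroids, 5-ASA and thiopurines. Each is defined as concomitant use of listed drug codes, against none.

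SAP 6.4.4 has a default for uncertain start or stop dates: "For medications, the medication will be flagged as concomitant". Protocol 9.9 uses the word for drugs already being taken at entry: "Subjects taking concomitant medications should be on stable dosages at the time of baseline".

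**The concern.** The two definitions do not cover all cases. The case they leave out is the ordinary one in this trial: a patient who enters on long-standing azathioprine, mesalamine or prednisone and stays on it.

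Two outputs depend on the classification. In the 6.15.1 subgroups, users would be counted with non-users, so the comparison would no longer describe what its label says. In the concomitant-medication tables, the background therapy that protocol 7.2 relies on to justify a placebo control would be missing.

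SAP 6.1 gives efficacy outputs to the sponsor and most other outputs to a contract research organization. Two teams would therefore have to resolve the same contradiction separately, and the subgroups and the medication tables could disagree.

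**Working it through.** The plan states no figure on this point, so there is none to reproduce. The check has four steps.

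**1. Which date patterns are left out.** Apply the two 6.10 definitions, and the definitions proposed under the fix, to each pattern.

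| Start | Stop | 6.10 as written | Proposed |
|---|---|---|---|
| before consent | before consent | prior | prior |
| before consent | on the consent date or later in screening | neither | concomitant |
| on or before consent | ongoing | neither | concomitant |
| after consent | any | concomitant | concomitant |

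The first-dose sentence says that dates are compared but gives no decision rule. The allocation sentence places drugs already classed as concomitant; it does not bring new ones in. 6.10 also assigns to induction the concomitant use that starts and stops in screening, but a drug begun before consent and stopped in screening did not start there.

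**2. Thiopurines.** Inputs:
- Protocol 8.1 [9c] and Table AMAC.3: dose stable for at least 8 weeks (56 days) before baseline, and only if already taken at baseline.
- Protocol 7.1: "Subjects will be evaluated for study eligibility ≤ 28 days before the baseline visit". Consent is taken at Visit 1, so it falls at most 28 days before baseline.

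Days from start to consent ≥ 56 − 28 = 28. No compliant user with known dates can have a start after consent, so the number classed as concomitant is 0. Under 6.15.1, a category with less than 10% of the population gets descriptive statistics only. On about 240 patients that is 0.10 × 240 = 24, so the planned thiopurine tests would not be run.

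**3. 5-ASA and oral corticosteroids.** Inputs:
- Protocol 8.1 [9a] and [9b]: dose stable for at least 2 weeks before screening endoscopy.
- Protocol 8.1 [5]: Mayo score with endoscopic subscore within 14 days before first dose.

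Let consent be *c* days before first dose (0 to 28) and endoscopy *e* days before (0 to 14, *e* ≤ *c*). Take the date of the current dose as the start, which is the reading kindest to the SAP. The start is then at least *e* + 14 days before first dose. To be concomitant it must be fewer than *c* days before.

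Qualifying start days = max(0, *c* − *e* − 14).

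- *c* = 28, *e* = 0: 28 − 0 − 14 = 14 days, the maximum.
- *c* = 28, *e* = 7: 7 days.
- *c* = 28, *e* = 14, or any *c* ≤ 14: 0 days.

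These groups are depleted but not necessarily empty. A later dose change entered as a new record would qualify from its own date only. The documents give no start dates, so the number lost cannot be computed.

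**4. Side note on SAP 6.16.** For the deviation checks, a partial stop date of a prior drug is set to the first of the month or to 1 January. The imputed stop is never later than the true one, so in a washout check it can hide a violation but cannot create one. As an illustration with invented dates, take a true stop on 20 June, recorded as June only, and randomization on 1 August. The true gap is 10 + 31 + 1 = 42 days, inside the 56-day anti-TNF window. The imputed gap from 1 June is 30 + 31 = 61 days, outside it.

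**The case against.** The strongest reply is that the intended meaning is plain. 6.10 compares dates with first dose and speaks of drugs that are ongoing. 6.15.1 heads the subgroups as baseline medication and describes current use, and protocol 9.9 calls stable background drugs concomitant. A competent programmer would probably classify them so. SAP 6.4.4 also flags drugs with doubtful dates as concomitant, so some thiopurine users could be counted correctly even under the definitions as written. The subgroups carry no multiplicity adjustment and are supportive only.

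Much of this stands. It limits the claim to patients with known dates and makes this an inconsistency with a recoverable intent. It does not remove the problem. The only sentences that say what prior and concomitant mean give the wrong answer for background therapy. The 6.4.4 default does not reach a documented start date, and 6.18 removes the protocol's medication summary as a fallback. The SAP's revision history also records a change of the concomitant start-date definition from first dose to consent. That is history and not itself an error, but it gives a programmer reason to take the consent-date sentence as deliberate.

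A reader might infer that the planned thiopurine group is empty. The documents do not support that: it is empty only if the definitions are applied alone, to compliant patients with known dates.

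**Conclusion.** The point holds as an internal inconsistency that should be corrected. The 6.10 definitions are wrong as written for ordinary background therapy; this is more than missing detail. Programmed literally, they leave no compliant thiopurine user with known dates in the user group, probably misplace most 5-ASA and oral corticosteroid users, and take background UC therapy out of the concomitant tables. The thiopurine result rests on the 8-week and 28-day limits; the 14-day ceiling rests on treating the current-dose date as the start date.

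Three stronger readings are not supported.

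- **That the main result is affected.** The primary analysis is ITT and adjusts for region and prior biologic experience. The prior-biologic subgroup comes from a case report form question. None uses the 6.10 classes.
- **That a share of 5-ASA or steroid users lost can be stated.** Of the 330 whole-day pairs of *c* and *e*, 105 leave any qualifying window and 225 leave none. That counts date pairs with equal weight; it is not a frequency among patients.
- **That 6.16 has a known miss rate.** The number of partial dates is not given, and monitoring is a second source of eligibility deviations. The 30-day cyclosporine/thalidomide check is anchored to randomization in the Table 9 footnote but to screening endoscopy in exclusion [14a]. The consequence is confined to the deviation listing and a sensitivity analysis that SAP 6.2 leaves optional.

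**What to change.** - **SAP 6.10.** Define prior as stopped before the consent date, and concomitant as taken on or after the consent date whatever the start date. Assign a concomitant drug to each period in which it is ongoing, and report drugs stopped during screening with induction. Keep the 6.4.4 default for doubtful dates.
- **SAP 6.15.1.** Define the baseline UC-medication subgroups as use on the date of first dose.
- **SAP 6.16 (side note).** List for medical review any partial stop date that could fall inside a washout window, instead of letting the earliest-date rule settle it.

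The first two changes cost one sentence each and minor programming. The third adds some cases to review; how many depends on the number of partial dates. None alters the design, data collection, clinical management or the primary analysis.
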